Scientific Research Council of Alanya Alaaddin Keykubat University

**INVESTIGATION OF CANDIDATE miRNAs AS POTENTIAL BIOMARKERS IN
THE THE EARLY DIAGNOSIS OF PROSTATE CANCER AND BENIGN PROSTATE
HYPERPLASIA**

Project number

2020-04-03-MAP01

Project Team

Assoc. [name]. [name] (Correspondence)

Investigators

[name] [name]

[name] [name]

Assoc. [name]. [name]

Assoc. [name]. [name]

The Clinical Research Ethics Committee of the Alanya Alaaddin Keykubat University Faculty
of Medicine

(Ethical Approval No. 10354421-2020/16-24)

(Ethical approval date : 13.02.2020)

Objective and Scope

Prostate cancer (PCa) is one of the most common cancers in men and the second highest cause of cancer-related deaths (Vanacore et al, 2017; Siegel et al., 2019). Early diagnosis of cancer is very important for the clinical evaluation of the patient and selective and effective treatment. Currently, PCa is diagnosed by serum prostate-specific antigen (PSA) measurements, digital rectal examination (DRE) and pathologic evaluation of prostate biopsies performed under transrectal ultrasonography guidance (Bhagirath et al., 2018). PSA value should be measured at least twice for biopsy decision. Although PSA is a guide in the diagnosis of PCa, its level can also be increased in benign conditions such as benign prostatic hyperplasia (BPH) and prostatitis (Abramovic, 2020). Nevertheless, the free/total (f/t) PSA ratio of 4-10 ng/ml is recommended to differentiate between BPH and prostate cancer (Bhagirath et al., 2018; Vanacore et al., 2017; Siegel et al., 2019). However, the PSA level does not provide reliable results and is lower than the determined value in some cancer patients or considerably higher in some BPH patients. This leads to a large number of patients being biopsied unnecessarily or some patients being missed (Abramovic, 2020; Szelisk et al., 2018). More specific, sensitive, and reliable biomarkers are needed in the clinic to aid pre-treatment decision-making, especially to better distinguish malignant from non-malignant conditions, as well as aggressive from non-aggressive tumors (Abramovic, 2020).

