2.1. Study Design and Patients

The study included 20 PCa patients and 17 BPH patients who are clinically and pathologically confirmed, aged between 40-70 years, with serum PSA levels above 4 ng/mL, who presented to the urology clinic between January 2021 and December 2022. Additionally, 20 healthy volunteers who visited the urology outpatient clinic for routine check-ups were included in the study as the control group. Patients who had undergone drug therapy or surgery for prostate cancer had chronic inflammatory or infectious diseases, were hospitalized within the past year for a chronic illness, or had another known malignancy were excluded from the study.

The Clinical Research Ethics Committee of the Alanya Alaaddin Keykubat University Faculty of Medicine granted ethical approval (Approval No. 13.02.2020/16-24), and informed consent was obtained from all participants.

The clinical diagnosis of patients included in the study was conducted at the Urology Outpatient Clinic of Alanya Alaaddin Keykubat University Training and Research Hospital, with pathological assessments performed in the Pathology Laboratory of the same institution. Serum PSA levels were determined using the ELISA method, and miRNA expression analyses were performed using quantitative real time polymerase chain reaction (qRT- PCR) following miRNA isolation from peripheral blood samples.

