2.1.1. Study Criteria

Inclusion Criteria:

- For all groups, between 40-70 years of age.
- Prostate cancer group: Patients with positive digital rectal examination (DRE) results, serum PSA level above 4 ng/mL and a confirmed pathological diagnosis of Prostate cancer.
- BPH group: Patients with a PSA level over 4 ng/mL and a negative DRE result who were clinically and pathologically diagnosed with BPH.
- Control: Healthy volunteers who applied to the urology outpatient clinic for routine check-ups and whose PSA value was below 4 ng/ml.

Exclusion Criteria:

- To have undergone drug therapy or surgery for prostate cancer,
- To have chronic inflammatory or infectious diseases,
- Were hospitalized within the past year for a chronic illness,
- To have another known malignancy,
- Being outside the age limit of 40-70.

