2.2. Blood Samples and PSA Levels

Two milliliters of peripheral venous blood were collected from the volunteers included in the study into EDTA tubes. Serum PSA immunoassays evaluated for clinical examinations were determined on the automated immunoassay analyser.

2.3. miRNA Expression with Quantitative Real-Time PCR Reaction (qRT-PCR)

miRNA was extracted from the peripheral blood samples of volunteers using the Hybrid-R™ miRNA Isolation Kit and applied the following steps according to the manufacturer's instructions. Subsequently, according to the manufacturer's instructions, miRNA was converted to cDNA using the miR cDNA Synthesis Kit. A total of 20 μ l volumes of reactions containing miRNA-specific stem-loop primers were performed for each sample.

The expression levels of miR-107, miR-134-5p, miR-149-5p, miR-370-3p, miR-221-5p were measured by quantitative real-time PCR using miRqGreen MasterMix and the reaction was performed according to the manufacturer's instructions. Expression levels of each miRNA were calculated using the comparative cycle threshold (ct) method according to the formula $2^{-\Delta\Delta Ct}$ (Livak & Schmittgen, 2001). The fold change ratio of each miRNA was determined and compared with that of the control.

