2.4. Statistical Analysis Plan (SAP)

All statistical analysis and graphs were performed using GraphPad Prism-5 (version 9.0) and SPSS 21.0 software. The normal distribution of the data was evaluated with the Shapiro-Wilk test. The results were expressed as mean \pm standard deviation ($x\pm SD$) for continuous variables such as age that showed normal distribution and as median (Interquartile range [IQR]) for continuous variables that did not show normal distribution, such as PSA levels. Categorical variables were compared using the chi-square test.

miRNA (miR-107, miR-134-5p, miR-149-5p, miR-370-3p, miR-221-5p) expression levels did not show normal distribution, and statistical analyses were performed using the Kruskal-Wallis or Mann Whitney-U test. The relationship between miRNAs and serum PSA levels and Gleason scores was analyzed using the Spearman correlation test.

The role of miRNAs as biomarkers in prostate cancer was investigated by drawing the receiver operating characteristic (ROC) curves and the area under the ROC curve (AUC), cut-off point, sensitivity and specificity for each miRNA was calculated. Statistical significance was taken as $p < 0.05$.

3. Important Dates

Ethical approval date : 13.02.2020

Study Start and Completion: June 1, 2020- March 2, 2023

Patient registration start and completion: 26.01.2021-05.12.2022

The project duration lasted 2 years and 9 months in total.

The project's final report was presented to the Scientific Research Council of Alanya Alaaddin Keykubat University on 02.03.2023. The final report was accepted at the board meeting dated 08.03.2023.

4. References

Aghdam SG, Ebraze M et all.(2019)The role of microRNAs in prostate cancer migration, invasion, and metastasis. *J Cell Physiol*, 234:9927-9942. <https://doi.org/10.1002/jcp.27948>

Cowland, J. B., Hother, C., & Gronbaek, K. (2007). MicroRNAs and cancer. *APMIS*, 115(10), 1090-1106. doi: 10.1111/j.16000463.2007.apm_775.xml.x.

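### The ROC plan gives per-miRNA cut-offs, sensitivity and specificity with no comparator, cut-off rule, confidence interval or internal validation, so large imprecision, and possibly some optimism, would go unseen

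*Combined protocol and SAP*

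**What the plan says.** The ROC plan is one sentence at the end of section 2.4. It begins "The role of miRNAs as biomarkers in prostate cancer was investigated by drawing the receiver operating characteristic (ROC) curves" and ends by stating that "the area under the ROC curve (AUC), cut-off point, sensitivity and specificity for each miRNA was calculated". The section then sets significance at p < 0.05. It says nothing about the reference group, how a cut-off is picked, whether higher or lower expression counts as positive, intervals or validation.

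Three comparisons are possible from section 2.1: "The study included 20 PCa patients and 17 BPH patients", and "20 healthy volunteers who visited the urology outpatient clinic for routine check-ups were included in the study as the control group". No second cohort is described.

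The non-cancer groups are defined differently in section 2.1.1. BPH men are "Patients with a PSA level over 4 ng/mL and a negative DRE result"; controls are men "whose PSA value was below 4 ng/ml". The one mention of a reference near the assay is in section 2.3: "The fold change ratio of each miRNA was determined and compared with that of the control". That concerns fold change, not the ROC curves.

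**The concern.** ROC analysis is the method section 2.4 names for judging the miRNAs as prostate cancer biomarkers, so its outputs carry the diagnostic conclusion. Two things are at stake.

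**Meaning.** A sensitivity and specificity pair cannot be interpreted without its comparator. Cancer patients and BPH patients both have PSA above 4 ng/mL, while controls are below 4. Cancer against control therefore contrasts groups already separated by PSA. Cancer against BPH is the contrast in which PSA is known to struggle. The Objective and Scope section describes the clinical need as markers "especially to better distinguish malignant from non-malignant conditions".

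**Reliability.** With 20 cases and 17 to 37 comparators, each proportion is very imprecise, and the plan calls for no interval. With no other cohort described, the natural reading is that the cut-off is chosen and scored in the same men. Under rules that maximise accuracy in the sample, that also biases sensitivity and specificity upward.

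**Working it through.** The plan states no target AUC, expected accuracy or sample-size calculation, so there is no figure of its own to reproduce.

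**Inputs from the documents:** 20 PCa, 17 BPH and 20 controls (section 2.1), hence 17 + 20 = 37 if pooled; five miRNAs (section 2.4).

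**Assumed, because the documents give none:** the illustrative counts 16/20, 13/17 and 28/37; an illustrative AUC of 0.80; binormal marker values with equal variances; true AUC 0.60 to 0.90.

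**Step 1. Precision of sensitivity and specificity.** Clopper-Pearson 95% limits for x of n are the 2.5% quantile of Beta(x, n − x + 1) and the 97.5% quantile of Beta(x + 1, n − x).

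| Count | Estimate | Exact 95% CI |
|---|---|---|
| 16/20 | 80% | 56% to 94% |
| 13/17 | 76% | 50% to 93% |
| 28/37 | 76% | 59% to 88% |

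**Step 2. Precision of the AUC.** Hanley-McNeil: SE² = [A(1 − A) + (n₁ − 1)(Q₁ − A²) + (n₀ − 1)(Q₂ − A²)] / (n₁n₀), with Q₁ = A/(2 − A) and Q₂ = 2A²/(1 + A). For A = 0.80, Q₁ − A² = 0.6667 − 0.64 = 0.0267 and Q₂ − A² = 0.7111 − 0.64 = 0.0711.

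- 20 vs 17: (0.160 + 0.507 + 1.138)/340 = 0.00531; SE 0.073; 95% CI 0.66 to 0.94.
- 20 vs 20: (0.160 + 0.507 + 1.351)/400 = 0.00504; SE 0.071; 95% CI 0.66 to 0.94.
- 20 vs 37: (0.160 + 0.507 + 2.560)/740 = 0.00436; SE 0.066; 95% CI 0.67 to 0.93.

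**Step 3. Optimism if an accuracy-optimising rule was used.** Monte Carlo, 20,000 studies per setting, direction fixed, cut-off midway between adjacent observed values. Optimism is the apparent value minus the true value at the chosen cut-off, in percentage points, as true AUC goes from 0.60 to 0.90.

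| Comparison | Rule | Sensitivity | Specificity |
|---|---|---|---|
| 20 vs 17 | Maximum Youden | 8.0 to 5.4 | 9.4 to 6.4 |
| 20 vs 20 | Maximum Youden | 8.4 to 5.4 | 8.4 to 5.5 |
| 20 vs 37 | Maximum Youden | 9.7 to 6.5 | 5.2 to 3.4 |
| 20 vs 17 | Closest to corner | 5.9 to 4.4 | 6.9 to 5.3 |
| 20 vs 20 | Closest to corner | 6.1 to 4.6 | 6.1 to 4.6 |
| 20 vs 37 | Closest to corner | 6.9 to 5.2 | 3.8 to 2.8 |

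The range is 2.8 to 9.7 points. Example: for 20 vs 17, true AUC 0.75 and Youden, apparent sensitivity and specificity average 73% and 75%, against 66% and 67% in new patients. Unequal variances (SD ratio 0.67 or 1.5) gave 2.8 to 8.4.

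**Step 4. How far this depends on the rule and on selection.**

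- Sensitivity set equal to specificity: about 0 to 1 point.
- Sample sensitivity or specificity held at 90% or more: about 1 to 4.5 points.
- Direction chosen from the data and the best of five independent markers highlighted (20 vs 17, Youden, equal true AUC 0.5 to 0.8): about 12 to 19 points.
- The AUC of one marker with direction fixed is not biased. Under the same best-of-five selection it is: a true AUC of 0.60 appears as 0.71 on average.

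**Step 5. Whether the remedies work at this size.** Ordinary exact 95% intervals at the data-chosen cut-off still contained the true value in 92.5% to 97.0% of studies (Youden) and 95.2% to 97.4% (closest to corner). Bootstrap optimism correction removed 61% to 66% of the bias (Youden) and 61% to 71% (closest to corner).

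**The case against.** The strongest reply has four parts.

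*No rule is stated, so no bias figure can be attached to the plan.* This stands. A reader might infer that any cut-off picked in the same men overstates accuracy by 3 to 10 points. Step 4 shows that this is too general: some rules give almost no optimism. Nor is 10 a ceiling, because section 2.4 does not fix direction and the protocol's introduction notes conflicting reports on whether various miRNAs are up- or downregulated.

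*The study is finished.* This also stands. Section 2.4 is in the past tense and section 3 records that the final report was accepted in March 2023. A reader might infer that the results were published without intervals or with inflated accuracy. The documents contain no results and do not show what was reported.

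*It is a small study meant to inform later biomarker work, so internal validation is optional.* This stands in part. Step 5 shows that plain intervals deal with most of the problem, and no passage proposes clinical use of a cut-off. But the plan does not label its cut-offs exploratory.

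*The sentence about malignant and non-malignant conditions is background.* True: it also mentions aggressive against non-aggressive tumours, and it does not set the ROC contrast. It shows why the choice of comparator matters, not which one was made.

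None of this supplies the missing comparator, rule or intervals.

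**Conclusion.** The point holds as a gap in the plan, and should be fixed. Section 2.4 leaves out the ROC comparator, cut-off rule, intervals and internal validation, and no other section supplies them. That rests on the text alone.

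Imprecision is the larger consequence. At 16/20 the lower limit lies 24 points below the estimate (80 − 56), more than twice the largest optimism in the Step 3 table. The intervals assume only the illustrative counts and AUC.

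Optimism of about 3 to 10 points is conditional on maximum Youden or closest-to-corner, the same men, a fixed direction, a binormal marker and a true AUC of 0.60 to 0.90. Outside those conditions it may be near zero or above 10. Confidence is high in the omission and moderate in the size of the bias. The documents do not support a statement that reported accuracy was in fact inflated.

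**What to change.** In section 2.4, state what was done: the comparator for each ROC curve, with PCa vs BPH and PCa vs control reported separately; the cut-off rule; and the marker direction, saying whether it was set in advance or from the data. Then add wording such as:

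> For each miRNA and each comparison, the AUC is reported with a 95% CI, and apparent sensitivity and specificity at the cut-off with exact 95% CIs. Bootstrap optimism-corrected estimates are given alongside, repeating the cut-off choice (and the choice of direction, if made from the data) in each resample. Analyses not in the original plan are labelled post hoc. Cut-offs are exploratory until validated in an independent cohort.

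The minimum is the comparator, rule, direction, intervals and exploratory label; the bootstrap correction is a cheap addition.

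The cost is a few sentences and a short re-analysis of existing data, with no new patients or assays. The reported accuracy will look less favourable. The correction is only partial, leaving about 30% to 40% of the optimism, and it does not address highlighting the best of five markers unless that selection is also repeated in each resample.
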